**Table 6. Dose Modifications for Related Hematologic Toxicities**

Criteria	Severity	Dosage modification
Neutropenia  ANC <1000/ $\mu$ l for at least 7 days  or  ANC <500/ $\mu$ l  or  ANC <1000/ $\mu$ l with a single temperature of >38.3 °C or a sustained temperature of $\geq$ 38 °C for more than one hour	G3/4	
Withhold PF-07901801, tafasitamab and lenalidomide and monitor CBC at least weekly until ANC is <math>\geq</math>1000/<math>\mu</math>l, then:
 

• Resume PF-07901801 and tafasitamab at the same dose;

• Reduce lenalidomide by one dose level:

◦ See Section 6.9.4 regarding use of hematopoietic growth factors.

◦ Repeat as above for a subsequent event. After second dose reduction of lenalidomide and a subsequent event, discuss with sponsor for further dose modification options.

Thrombocytopenia	G3/4	
Withhold PF-07901801, tafasitamab and lenalidomide and monitor CBC at least weekly until platelet count is <math>\geq</math>50000/<math>\mu</math>l or baseline, then:
 

• Resume PF-07901801 and tafasitamab at the same dose;

• Reduce lenalidomide by one dose level:

◦ Repeat as above for a subsequent event. After second dose reduction of lenalidomide and a subsequent event, discuss with sponsor for further dose modification options.

Thrombocytopenia $\geq$ G3 with $\geq$ G2 bleeding	$\geq$ G3	
Withhold PF-07901801, tafasitamab and lenalidomide and monitor CBC at least weekly until platelet count is <math>\geq</math>50000/<math>\mu</math>l or baseline and bleeding has stopped, then:
 

• Resume PF-07901801 and tafasitamab at the same dose;

• Reduce lenalidomide by one dose level:

◦ Repeat as above for a subsequent event. After second dose reduction of lenalidomide and a subsequent event, discuss with sponsor for further dose modification options.

PFIZER CONFIDENTIAL

CT02-GSOP Oncology Clinical Protocol Template (01 April 2022)

Page 75

**Table 6. Dose Modifications for Related Hematologic Toxicities**

Criteria	Severity	Dosage modification
Anemia	G3/4	
Withhold PF-07901801, tafasitamab and lenalidomide and monitor CBC at least weekly until hemoglobin is <math>\geq 8</math> g/dL, then:
 

• Resume PF-07901801 and tafasitamab at the same dose;

• Reduce lenalidomide by one dose level:

◦ See Section 6.9.4 regarding use of hematopoietic growth factors.

◦ Repeat as above for a subsequent event. After second dose reduction of lenalidomide and a subsequent event, discuss with sponsor for further dose modification options.

**Table 7. Dose Modifications for Non-Hematologic Toxicities**

Criteria	Severity	Dosage modification
Non-hematologic laboratory events considered related to study treatment(s)	≥G3	

Hold suspected therapy(ies) until resolution to ≤G2 or baseline or to a level determined to be acceptable by the investigator.

Lenalidomide may be reduced by one dose level. See also SmPCs for MINJUVI (tafasitamab) and REVLIMID (lenalidomide).

Transient, asymptomatic, G4 laboratory abnormalities considered not clinically significant may not require a dose reduction following agreement between investigator and the sponsor.

Abnormal liver tests (related or unrelated)	≥G2	

Participants who present with elevated AST/ALT and bilirubin must be evaluated further as potential DILI (Hy's law) cases to definitively determine the etiology of the abnormal laboratory values; evaluation is to occur as soon as possible, preferably within 48 hours of the abnormal results. See Liver Safety Guidelines for follow-up of possible DILI (Appendix 6).

Abnormal liver tests (related or unrelated)	≥G3	

Hold suspected therapy(ies) until resolution to ≤G2 or baseline or to a level determined to be acceptable by the investigator.

Lenalidomide may be reduced by one dose level. See also SmPCs for MINJUVI (tafasitamab) and REVLIMID (lenalidomide).

Participants who present with elevated AST/ALT and bilirubin must be evaluated further as potential DILI (Hy's law) cases to definitively determine the etiology of the abnormal laboratory values; evaluation is to occur as soon as possible, preferably within 48 hours of the abnormal results. See Liver Safety Guidelines for follow-up of possible DILI (Appendix 6).

**Table 7. Dose Modifications for Non-Hematologic Toxicities**

Criteria	Severity	Dosage modification
Other Non-hematologic AEs (related)	G3	

Hold suspected therapy(ies) until resolution to <math>\leq</math>G1 or baseline or to a level determined to be acceptable by the investigator.

Lenalidomide may be reduced by one dose level. See also SmPCs for MINJUVI (tafasitamab) and REVLIMID (lenalidomide).

 
Exceptions (do not require dose modifications, manage symptoms as per institutional standard of care):
 

G3 nausea, vomiting, and diarrhea resolved to <math>\leq</math>G1 or baseline within 48 hours with supportive care;

Transient G3 fatigue (lasting <72 hours).

Other Non-hematologic AEs (related)	G4	

Consider permanently discontinuing the suspected therapy(ies). In the case where the investigator determines the participant is obtaining a clinical benefit, discuss with sponsor for further dose modification options.

Hold suspect therapy(ies) until resolution to <math>\leq</math>G1 or baseline or to a level determined to be acceptable by the investigator. When resumed after interruption, lenalidomide is to be reduced by one dose level. See also SmPCs for MINJUVI (tafasitamab) and REVLIMID (lenalidomide).

**Table 8. Dose Modifications for Lenalidomide Toxicities**

Criteria	Severity	Dosage modification
Thromboembolic events (related)	G3/4	
 
Interrupt lenalidomide dosing. Start anticoagulation as per local guidelines.
 
Continue other study interventions after discussion with the sponsor.
 

	Toxicities resolve to $\leq$ G2	
 
Restart lenalidomide at investigator's discretion
 

Allergic reaction or hypersensitivity (related)	>G2	
 
Interrupt lenalidomide dosing. Follow at least every 7 days.
 
Continue other study interventions as per protocol.
 

	Toxicities resolve to $\leq$ G2	
 
Restart lenalidomide at next lower dose level.
 

Allergic reaction or hypersensitivity (including but not limited to SJS, TEN, exfoliative or bullous rash, angioedema) (related)	G3/4	
 
Discontinue lenalidomide permanently.
 
Continue other study interventions after discussion with the sponsor.
 

Desquamating (blistering) rash $\geq$ G3 or non-desquamating rash G4 considered to be related to lenalidomide		
 
Discontinue lenalidomide permanently.
 
Continue other study interventions after discussion with the sponsor.
 

Non-desquamating rash (related)	G3/4	
 
Interrupt lenalidomide dosing.
 
Continue other study interventions after discussion with the sponsor.
 

	Toxicities resolve to $\leq$ G1	
 
Restart lenalidomide at next lower dose level.
 

Tumor flare reaction (related)	G1/2	
 
Provide symptomatic treatment as per local guidelines.
 
Continue lenalidomide without dose modifications or interrupt as per investigator's discretion.
 
Continue other study interventions as per protocol.
 

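### Protocol Table 8 gives opposite lenalidomide instructions for related hypersensitivity at G3/4 and related non-desquamating rash at G4, and no text says which row prevails

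*Protocol*

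**What the plan says.** All the conflicting text is in Table 8 of the protocol, under Section 6.6.1.

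- **Related hypersensitivity, graded >G2.** "Interrupt lenalidomide dosing. Follow at least every 7 days". When the event has resolved to G2 or less: "Restart lenalidomide at next lower dose level".
- **Related hypersensitivity, graded G3/4**, headed "Allergic reaction or hypersensitivity (including but not limited to SJS, TEN, exfoliative or bullous rash, angioedema) (related"). The instruction is "Discontinue lenalidomide permanently".
- **Rash, permanent-stop row.** This covers desquamating rash of G3 or worse and "non-desquamating rash G4 considered to be related to lenalidomide". Lenalidomide is stopped for good.
- **Rash, interrupt-and-restart row**, headed "Non-desquamating rash (related") and graded G3/4. Lenalidomide is held, then restarted one level lower at G1 or less.

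The risk assessment in Section 2.3.1 lists angioedema, anaphylactic reaction, SJS, TEN and DRESS as lenalidomide risks. Its mitigation sends the site to Table 8 for dose changes and to the SmPC for more detail.

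**The concern.** This is a safety-rule point rather than a point of statistical method. A site facing G3 or G4 hypersensitivity, or G4 non-desquamating rash, attributed to lenalidomide can find one row that ends the drug and another that allows rechallenge. The risk lies with the site that follows the restart row; a site that stops is already within the table.

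The exposed cases are mainly G3/4 hypersensitivity reactions that the stop row does not name, and G4 non-desquamating rash. Anaphylactic reaction and DRESS are examples of the first kind: Section 2.3.1 lists both, and the stop row names neither.

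There is a smaller administrative effect. Section 8.4.10 counts failure to make a required dose modification as a medication error. For these events the table does not settle what is required.

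**Working it through.** No sample size, power or rate is involved, so the check is to list the grades each row covers, find the overlaps, and look for a rule that resolves them.

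**Step 1: coverage.** The grade >G2 means G3 and above. For related events:

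| Event | Grade | Permanent-stop row | Restart row | Conflict |
|---|---|---|---|---|
| Hypersensitivity | G3 | G3/4 row | >G2 row, at ≤G2 | Yes |
| Hypersensitivity | G4 | G3/4 row | >G2 row, at ≤G2 | Yes |
| Desquamating rash | G3 | ≥G3 row | No competing rash row | No |
| Desquamating rash | G4 | ≥G3 row | No competing rash row | No |
| Non-desquamating rash | G3 | None | G3/4 row, at ≤G1 | No |
| Non-desquamating rash | G4 | G4 row | G3/4 row, at ≤G1 | Yes |

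Three events × two grades = 6 combinations, of which 3 conflict. This count describes the table; it does not measure risk to participants.

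**Step 2: size for one participant.** Table 10 puts 20 mg directly below the 25 mg starting dose. After recovery, one row gives 20 mg on dosing days and the other gives 0 mg.

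**Step 3: search for a tie-breaker.**

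- Sections 6.6 and 6.6.1 base modification on the worst toxicity. That selects the event and grade to act on. Here a single event at a single grade has two instructions.
- Section 6.6.1 takes the lenalidomide dose at resumption from the tables, unless investigator and sponsor agree otherwise. That leads back to the same rows.
- Table 7, for other related G4 events, asks only that permanent discontinuation be considered.
- Section 6.6.2 sets the recovery needed before re-treatment: baseline or G1 for related non-laboratory toxicity. It governs when a restart may happen, not whether one is barred. It is also stricter than the G2 threshold in the hypersensitivity restart cell.
- Sections 6.1.1.3 and 6.6.1 refer to the lenalidomide SmPC without saying that it overrides Table 8.

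None of these ranks the rows.

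**Step 4: could >G2 be a misprint?** If G2 or worse was meant, the overlap at G3 and G4 remains. If G2 alone was meant, the overlap disappears, but the printed restart condition of G2 or less would already be met at onset. The printed >G2 fits its paired cell. The layout, a general row followed by a separate G3/4 row, points towards G2. The documents do not settle which was intended.

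**The case against.** Four arguments against the point deserve an answer.

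**Specific over general.** For G4 non-desquamating rash, a reader may prefer the row that names G4 to the one graded G3/4. That is a sensible reading, but it is not written down. It does not help with hypersensitivity, where the stop row's list is non-exhaustive and both rows cover the whole class.

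**The SmPC governs.** Section 6.1.1.3 requires lenalidomide to be given according to the SmPC. The SmPC is not among the documents, so whether it would settle the choice cannot be checked. What can be said is that Section 2.3.1 names Table 8 for dose changes and no text gives the SmPC precedence.

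**Section 6.6.2 already bars restart at G2.** It does, and this stands. It delays the restart to baseline or G1 without preventing rechallenge.

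**Exposure is small.** This also stands. Lenalidomide runs for at most 12 cycles (12 × 28 = 336 days if no cycle is delayed), Phase 2 will not start, and the study is being terminated. Section 10.1.10 lets participants continue treatment after a termination unrelated to safety, so residual use is possible.

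Two stronger readings are tempting, and the documents support neither. A reader might infer that a site could restart lenalidomide after SJS or TEN and still comply. The stop row names SJS, TEN, exfoliative or bullous rash and angioedema, and desquamating rash of G3 or worse has no competing rash row, so a restart there would breach an express instruction. A reader might also infer that the two hypersensitivity rows conflict on the other study drugs, because one says "Continue other study interventions as per protocol" and the other "Continue other study interventions after discussion with the sponsor". Holding the discussion satisfies both.

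**Conclusion.** The point holds for lenalidomide only. Table 8 gives incompatible instructions for related hypersensitivity at G3 and G4 and for related non-desquamating rash at G4, and nothing in the protocol resolves them. That is 3 of the 6 combinations examined, with a consequence of 20 mg or nothing for a participant at the starting dose.

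The conclusion rests on the printed row labels and on reading >G2 as G3 and above. It does not depend on what the SmPC says, beyond the absence of any stated precedence. The number of participants still on lenalidomide is not given, and the documents report no such event in this study. It should be fixed because the conflict sits in a table the protocol relies on for mitigation and the edit is small.

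**What to change.** (a) In the non-desquamating rash interrupt-and-restart row, change the severity from G3/4 to G3. G4 then falls only under the permanent-stop row.

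(b) Make permanent discontinuation the only lenalidomide instruction for related hypersensitivity at G3/4. There are two ways to do this, and the sponsor's clinical team should choose:

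- Delete the >G2 row and its restart cell, and move the follow-up of at least every 7 days to the G3/4 row so that it is not lost. G2 hypersensitivity then has no row of its own, as is already the case.
- If the team confirms that G2 was intended, change >G2 to G2 and set the restart condition to baseline or G1, to match Section 6.6.2. The general statement in Section 6.6.1 that no specific adjustment is recommended for grade 1 or 2 events does not rule this out: Table 8 already reduces lenalidomide for G2 kidney toxicity, and Table 9 interrupts the infusion for a G2 infusion-related reaction.

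Under either choice the count of conflicts falls from 3 of 6 to 0 of 6. The cost is a few table cells, issued by letter or amendment as the sponsor decides, with no added data, visits or participants.

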**Table 8. Dose Modifications for Lenalidomide Toxicities**

Criteria	Severity	Dosage modification
Tumor flare reaction (related)  Kidney toxicities as per CTCAE v5.0 (test can be repeated after proper hydration, if needed) (related or unrelated)	G3/4	
 
Interrupt lenalidomide dosing.
 
Provide symptomatic treatment as per local guidelines.
 
Continue other study interventions after discussion with the sponsor.
 

	Toxicities resolve to $\leq$ G1	
 
Restart lenalidomide (maintain same dose level).
 

	G2	
 
Reduce lenalidomide to 10 mg once daily.
 

	G3 not requiring dialysis	
 
Administer lenalidomide at 15 mg every other day.
 
Discontinue lenalidomide if dialysis is required.
 

	G4	
 
Discontinue lenalidomide.
 

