### 6.6.1. Dose-Modification Guidelines

All dose modifications should be based on the worst preceding toxicity and must be recorded on the CRF. Dose modifications for tafasitamab are further described in MINJUVI (tafasitamab) SmPC; for dose modifications regarding lenalidomide consult the Revlimid® SmPC.

[Table 6](#) through [Table 9](#) provide dose modifications in case of hematologic and non-hematologic toxicities. Permitted dose reductions for lenalidomide are outlined in [Table 10](#). When dosing is withheld based on the following criteria outlined below, clinical and laboratory re-evaluation should be repeated at least weekly or more frequently per institutional guidelines until the toxicity resolves as per toxicity recommendation; see also [Appendix 6](#) (Hy's law). In events where there are transient lab value abnormalities that, based on investigator assessment, are not clinically significant or are related to disease and not the drug, continuation of therapy without following the dose-modification guidelines is permissible.

No specific dose adjustments are recommended for grade 1 or 2 treatment-related toxicity. However, investigators should always manage their participants according to their medical judgment based on the particular clinical circumstances.

Once a lenalidomide dose has been reduced for a given participant, all subsequent cycles will be administered at that dose level, unless further dose reduction is required. Intraparticipant dose re-escalation is not allowed.

Participants in Phase 1b experiencing a DLT may reduce PF-07901801 dosing and resume at the next lower dose level (if applicable) once adequate recovery is achieved, and in the

opinion of the investigator and sponsor, the participant is benefiting from therapy. In Phase 2, PF-07901801 toxicities are managed only with dose interruption (not reduction, unless expressly agreed otherwise following discussion between the investigator and the sponsor).

Appropriate follow-up assessments must be done until adequate recovery occurs as assessed by the investigator. Criteria required before treatment can resume are described in [Section 6.6.2](#).

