**Table 10. Reductions for Lenalidomide**

Starting dose	25 mg
DL1	20 mg
DL2	15 mg
DL3 (starting dose for moderate renal impairment)	10 mg
DL4	5 mg
DL5 a	2.5 mg

a. Patients who cannot tolerate DL5 are to be discontinued from lenalidomide treatment in the study but should continue PF-07901801 and tafasitamab.

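### Table 8's kidney rows name fixed lenalidomide doses above the 5 mg and 2.5 mg levels despite the no-re-escalation rule, and for a related grade 3 kidney laboratory event Tables 7 and 8 disagree on holding

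*Protocol*

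**What the plan says.** Protocol Table 8 has three kidney rows, and they apply whether or not the event is related to treatment. Grade 2: "Reduce lenalidomide to 10 mg once daily". Grade 3 not requiring dialysis: "Administer lenalidomide at 15 mg every other day". Grade 4, or a need for dialysis: lenalidomide stops.

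Table 10 lists the permitted lenalidomide levels as 25, 20, 15, 10, 5 and 2.5 mg. Its footnote shows that the lowest level is one a participant can actually be on: "Patients who cannot tolerate DL5 are to be discontinued from lenalidomide treatment in the study".

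Section 6.6.1 adds two rules. The first is "Once a lenalidomide dose has been reduced for a given participant, all subsequent cycles will be administered at that dose level", with an exception only for further reduction. The second is "Intraparticipant dose re-escalation is not allowed".

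For related non-hematologic laboratory events of grade 3 or higher, Table 7 says "Hold suspected therapy(ies) until resolution to" grade 2 or lower, baseline, or a level the investigator accepts. Section 6.6.2 then bars re-treatment after an interruption for related toxicity, or when a new cycle begins, until such laboratory toxicity is back to baseline or to grade 2 or lower.

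**The concern.** Where other Table 8 rows lower the dose, as for hypersensitivity and non-desquamating rash, they do so relative to the current level. The kidney rows name a fixed dose. A fixed dose is a reduction only for a participant who is above it, and Table 10 has two levels below both named regimens.

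Protocol Section 2.2.3.3.3 explains why this matters. Lenalidomide is eliminated mainly by the kidney, and clearance was 66% to 75% lower in moderate and severe impairment. The participants for whom the rows are ambiguous are those who have already needed reductions and now have falling renal function.

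The second issue is separate. A site facing a related grade 3 kidney laboratory event finds one table that says hold and another that names a dose to give. Protocol Section 8.4.10 counts failing to modify the dose as the protocol requires as a medication error, so a site that follows one table could be recorded as breaching the other.

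**Working it through.** **Inputs.** Named doses from Table 8; permitted levels from Table 10; dosing on Days 1 to 21 of a 28-day cycle from Protocol Section 6.1.1.3.

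**Check of the cycle convention.** SAP Section 6.6.3.3 gives an intended dose intensity of 525 mg per 4-week cycle. 25 × 21 = 525, so it reproduces.

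**Ratio of named dose to current dose.** The grade 2 ratio is 10 divided by the current daily dose. The grade 3 regimen averages 15 / 2 = 7.5 mg a day, so its ratio is 7.5 divided by the current daily dose.

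| Current daily dose (mg) | Grade 2 row: 10 / current | Grade 3 row: 7.5 / current |
|---|---|---|
| 25 | 0.40 | 0.30 |
| 20 | 0.50 | 0.375 |
| 15 | 0.67 | 0.50 |
| 10 | 1.0 | 0.75 |
| 5 | 2.0 | 1.5 |
| 2.5 | 4.0 | 3.0 |

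Both rows lower or maintain the dose at 10 mg and above. The excess is confined to 5 mg and 2.5 mg.

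**Total over Days 1 to 21.** Current dosing gives 21 × 5 = 105 mg or 21 × 2.5 = 52.5 mg. Table 8 does not state the start day of alternate-day dosing, so I assume 10 or 11 intakes, kept within Days 1 to 21.

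- 10 intakes: 150 mg; 150 / 105 = 1.43 and 150 / 52.5 = 2.86.
- 11 intakes: 165 mg; 165 / 105 = 1.57 and 165 / 52.5 = 3.14.

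**Related grade 3 kidney laboratory event, lenalidomide suspected.**

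| Provision | Action on lenalidomide | Way out |
|---|---|---|
| Table 7, laboratory row | Hold | Grade 2 or lower, baseline, or investigator-accepted level |
| Section 6.6.2 | No re-treatment after interruption or at a new cycle | Baseline, or grade 2 or lower |
| Table 8, grade 3 kidney row | Administer the named regimen | None needed |

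Nothing in Section 6.6 says whether Table 8 overrides Table 7 for kidney events. Section 6.6.2 also lacks the investigator-accepted exit that Table 7 offers.

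**The case against.** The strongest reply is that Section 6.6.1 already prevents the harm. It states "Intraparticipant dose re-escalation is not allowed", and an instruction to reduce cannot be carried out as an increase. This stands in part. A reader might infer that the protocol simply orders a dose increase during kidney toxicity, and the documents do not support that: the increase appears only when Table 8 is read without Section 6.6.1. But the grade 3 row says administer, not reduce, and neither row points to Section 6.6.1. Nor is the re-escalation rule absolute, since Section 6.1.1.3 allows a rise from 10 mg to 15 mg in moderate renal impairment. What remains is a contradiction between passages that the site must resolve for itself.

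The second reply is that Tables 7 and 8 are not opposed in general. That is correct. Table 7 holds only suspected therapies, only for related events, and lets the investigator accept another recovery level. A reader might infer a conflict for every grade 3 kidney event. There is none for unrelated events, or where lenalidomide is not suspected. Table 8 may well be meant as the more specific table, but no text says so.

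A reader might also set the grade 2 kidney row against the Section 6.6.1 sentence "No specific dose adjustments are recommended for grade 1 or 2 treatment-related toxicity". That sentence is a general recommendation, is followed by an appeal to medical judgment, and leaves room for specific rows such as the grade 2 infusion-reaction row in Table 9. I do not count it as a contradiction.

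Fixed renal doses are not in themselves a fault. The protocol ties 10 mg to moderate renal impairment consistently (Sections 2.2.3.3.3, 5.1 and 6.1.1.3, and Table 10).

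Finally, reach is small. Phase 1b entry requires creatinine clearance of at least 60 mL/min, and Phase 2 will not start. From 25 mg, 5 mg is four single-level steps down, fewer if the kidney row has already moved someone to 10 mg. For hematologic toxicity, Table 6 sends an event after the second reduction to sponsor discussion.

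**Conclusion.** The point holds in two limited parts. First, for a participant at 5 mg or 2.5 mg, the kidney rows name 2.0 or 4.0 times the current dose at grade 2, and on average 1.5 or 3.0 times at grade 3 (1.43 to 1.57 or 2.86 to 3.14 times over Days 1 to 21, depending on the assumed number of intakes). This conflicts with the grade 2 row's wording and with the re-escalation rule. Second, for a related grade 3 kidney laboratory event with lenalidomide suspected, Table 7 and Section 6.6.2 point one way and Table 8 the other, with no order of precedence.

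The point concerns safety instructions rather than any estimate. It matters only for Phase 1b participants still taking lenalidomide. The study is planned at approximately 20 in that phase, and Section 10.1.10 allows treatment to continue after a termination unrelated to safety. The entry limit on creatinine clearance does not rule out kidney toxicity on treatment. I read the grade 2, grade 3 without dialysis, and grade 4 lines as the kidney rows, and the grade 3/4 interruption line beside them as belonging to tumor flare.

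**What to change.** Reconcile the kidney rows of Table 8 with Table 7, Table 10, the carry-forward and re-escalation rules in Section 6.6.1, and the re-treatment conditions in Section 6.6.2. The revised text should state:

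- how each kidney row applies to a participant whose current lenalidomide dose is already below the dose named;
- which provision governs a grade 3 kidney laboratory event considered related when lenalidomide is a suspected therapy, including when a new cycle begins.

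Which dose or rule is right is for the sponsor's clinical team; this review proposes none. The cost is wording in two table rows and a cross-reference. With enrollment not proceeding to Phase 2, the sponsor could give sites with participants still on lenalidomide the clarification by administrative letter, the route it has already used for other clarifications.
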